## **F. Data Collection Methods**

All patients will be assigned a unique personal identifier that will not be linked to any patient identifying information. Data will be collected during the study in case report forms and then will be entered into a password-protected, secure database or automatically collected via the Regional Anesthesia Outcomes Database and uploaded to that same database.

With the exception of actigraphic data, all preoperative demographic information and intraoperative data will be extracted from the patients' EMR and loaded into the secure database.

Each subsequent day, appropriate data will be extracted from the EMR to the secure database for later analysis. In addition to the parameters described above, various other catheter-related and adverse outcome data points will be captured from the EMR and uploaded to the secure database for further analysis. Catheter boluses and catheter rate adjustments (if present) will be recorded as well.

Research information collected on paper (or other physical media) during the study will be stored in locked cabinets with access limited to the Principal Investigator and research personnel affiliated with the study. Information that has been generated as, or transferred to, electronic media will be kept on password protected, secured data servers. All health information is protected by HIPAA (Health Insurance Portability and Accountability Act) and all health records will be kept confidential. Patients' birthdate, name, and all other identifying information will be removed when analyzing and reporting the data. Any personal identifying information will be stored separately from the other information provided by or about the patient and no personal identifying information will be reported in any publications or presentations. Identifying information will be kept in a password protected, secure file with limited access by research personnel. Once data collection is complete, identifying information will be destroyed.

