In addition to observational tools and subjective scoring, patient functional status (activity, sleep quality and other measures) will be assessed by actigraphic analysis using the Fitbit™ Charge 3 smartwatch. A Fitbit™ will be placed on the non-dominant arm, if possible, after extubation on the day of surgery. The Fitbit™ will remain on the patient until discharge from the hospital (which on average is about 5 days post-op) and the actigraphic data subsequently will be downloaded to the secure research database and the data wiped from the device. If a study subject had an unforeseeable complication and they no longer progressed along the standard recovery path (e.g. re-intubation, return to ICU), or if the watch was interfering in clinical care in any way, the Fitbit™ would be removed.

Following primary data collection for the enrolled subjects, each subject will be matched by surgical procedure using the STS procedure code, to 2 patients within the cardiac surgery ERAS program QI database (IRB #P00029161 which allows retrospective data analysis of outcomes) by the research team. All patients recruited for this study are themselves already part of the enhanced recovery after cardiac surgery clinical program [QIP]. Matching will be performed 1:2 with respect to surgical procedure and diagnosis using the STS codes, within 30% of the study patient's age and according to gender (if possible) and will be blinded to outcomes. Thus, up to 90 additional patients will be included in this study, retrospectively in addition to the 45 study patients from the single arm interventional cohort study (BESB).

Groups will be compared for demographic data, risk factors (from the STS database), diagnosis, procedure and cardiopulmonary bypass and clamp times to ensure their similarities

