### **Secondary:**

- Analgesic requirements, rendered as total opiate equivalents, at 12, 24 and 48 hours, and the 24-hour period preceding both 72 and 96 hours postoperatively.
- Duration of intubation following OR exit.
- Duration of ICU stay following OR exit.
- Duration of inpatient admission.
- Median pain scores collected per standard of care (VAS, NRS, INRS, or FLACC) at 0-3h, 3-6h, 6-12h, 12-24h, 24-36h and 36-48h.
- Incidence of postoperative nausea and vomiting during the following time ranges: 0-6h, 6-12h, 12-24h, and overall
- Time to mobilization (e.g. up to chair, ambulation).
- Quality/Quantity of mobilization and sleep via postoperative actigraphy.
- Outcome and satisfaction measures associated with routine perioperative questionnaire responses.
- Adverse events. – catheter, hemodynamic instability during placement (new inotrope or vasopressor – including Ca, volume > 5ml/Kg, variation 10% baseline SBP and MAP)
- All major Society of Thoracic Surgeons (STS) standard indices of morbidity and mortality

\*Of note, all of the above data points are collected automatically (via the electronic medical record) for all patients, as a part of their routine clinical care, regardless of whether or not they participate in the study.

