### **Adverse Event Monitoring:**

Adverse outcomes will be carefully tracked for all patients enrolled in the study. Enrollment will be halted and the IRB informed by the PI if any of the following conditions are met:

- 1 of any of the following serious adverse events.
  - Patient death.
  - Pneumothorax directly resulting from placement or removal of the blocks and catheters as evidenced by: 1- lung puncture during placement resulting in a moderate to large pneumothorax on the side affected performed within 8 hours, and/or the development of a new air leak in an existing chest tube collection system. 2- The development of a new moderate to large pneumothorax within 8 hours after removal of Erector Spinae plane catheters.
  - Hematoma at the site of the catheter/block—causing pain or any neurological symptoms for the patient.
  - Persistent neurologic symptoms lasting more than 3 days after a single shot block or catheter is removed.

- Local anesthetic systemic toxicity (any symptoms leading to this diagnosis by a study team participant)
- >2 of any of the following minor/moderate adverse events in a given patient or >10 in aggregate:
  - Persistent bleeding at the site of the catheter insertion or block placement.
  - Leakage of local anesthetic from the catheter insertion site that leads to discontinuation of the catheter infusion.
  - Redness or superficial infection of the catheter site or site of the block placement.
  - Skin irritation at the site of the catheter insertion or block placement that results in greater than 3 cm of induration or is associated with pain.

In addition to these stoppage rules, we plan to have [name] MD (Director of Quality and Safety, Cardiac Surgery, BCH) independently review the case outcomes, etc. to ensure patient/subject safety in a way that may not be captured by the above stoppage rules. This monitor will make such assessments for each cohort of 15 patients. As [name] is not a part of the study team, these reviews need not be blinded/redacted/etc. in any way. Any concerns raised by [name] will be brought to the attention of the PI directly and the IRB as well in a timely fashion.

If there is a pause for any of the above reasons, continuance of the protocol will be at the discretion of the IRB in consultation with the study team. No individual care data will be reported unless there is a serious adverse effect. Reports will be done in an aggregated fashion.

*Special note regarding ropivacaine:*

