Ropivacaine use constitutes the standard of care at BCH for all nerve blocks and regional anesthetics, including cardiac surgical ERAS patients. Known potential adverse consequences of this mode of delivery of this medication include hypersensitivity, allergic reaction, hypotension and cardiac arrhythmias if injected intravascularly. The presence of any of these will be assessed by the primary anesthesiologist intraoperatively and treated appropriately at the time of block placement and initial bolus and further assessed for such daily by members of the research team and Acute Pain Service. Any occurrence of a possible adverse event or events will be documented and reported to the DSMB, the IRB and the Department of Anesthesia Quality Assurance Physician as appropriate. In the event

of a serious adverse event, it will be reported to the DSMB and IRB immediately and the study halted until a thorough investigation into the cause can be made.

The relative safety of ropivacaine for use in regional anesthesia is supported by the information contained the Pediatric Regional Anesthesia Network (PRAN) database. The PRAN is a consortium of major pediatric centers in North America that manages a prospective data registry on pediatric regional anesthesia. From their database, which at this time comprises more than 130,000 pediatric regional anesthetics from numerous major centers in the US and Canada, ropivacaine is documented to be used in greater than 85% of pediatric regional with a safety profile at least equivalent to, if not better than, bupivacaine.

Further, ropivacaine is very well studied in pediatrics. There is an extensive body of prospective clinical trials and clinical outcomes studies on ropivacaine pharmacokinetics, safety and clinical outcomes from infancy through adolescence. Our prescribing practices at BCH in the Regional Anesthesia and Acute Pain Services are derived from that body of PK information and consensus recommendations.

We therefore regard ropivacaine as the established standard of care for pediatric regional anesthesia and have selected it for use in this study.

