## **K. Data Analysis Plan**

At the time of data analysis, de-identified datasets will be downloaded from the secure database and merged into secure statistical analysis tool for purposes of analysis. Missing data will be accounted for when the data is coded into respective variables.

Descriptive statistics will be generated in order to summarize demographic characteristics of patients enrolled. Data will be tested for normality using the Shapiro-Wilk test. Data will be presented as total n (%), means and standard deviations (SD) if the distribution appears normal, or medians and range when not.

Assuming normality, t-tests will be conducted to investigate the differences between the two exposure groups (to compare total opioid equivalents, time required to place the block, time to extubation, and time to discharge, etc.). If data does not appear to be normal, Wilcoxon Rank Sum/Mann-Whitney tests will be used for group comparisons. Repeated measure analysis will be used to compare pain scores over time between groups and when compared to baseline values. Adverse events and complications (if any) associated with the blocks will be recorded and categorized. Fisher's exact test will be used to compare the proportion of patients who reported adverse events between the two groups.  $P<0.05$  will be considered statistically significant.

Should a clinically significant effect be demonstrated, healthcare costs related to the surgical encounter for both groups will be approximated and compared in order to better assess the added value of the intervention in a more global fashion.

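### The between-group Fisher test on adverse events may be biased against BESB: only enrolled patients are actively monitored, and the endpoint is largely made up of events that controls cannot have

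*Combined protocol and SAP*

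**What the plan says.** **Monitoring of enrolled patients.** Section I, under Adverse Event Monitoring, states: "Adverse outcomes will be carefully tracked for all patients enrolled in the study". The note on ropivacaine in the same section lists hypersensitivity, allergic reaction, hypotension and arrhythmia, and says patients are "further assessed for such daily by members of the research team and Acute Pain Service". Section D(3) puts every enrolled patient under Acute Pain Service follow-up at all hours.

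**Controls.** Section D(3) matches each enrolled patient "to 2 patients within the cardiac surgery ERAS program QI database", retrospectively. By Section D(1) these patients had no regional block. No tracking or daily assessment of them is described.

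**Endpoint.** The adverse-event item in Section E (Secondary) names catheter events and hemodynamic instability during placement. STS morbidity and mortality indices are a separate item in the same list.

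**Test.** Section K first says that block-associated adverse events will be recorded and categorized. It then says Fisher's exact test "will be used to compare the proportion of patients who reported adverse events between the two groups".

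**Sources.** The note closing the Section E list says "all of the above data points are collected automatically (via the electronic medical record) for all patients", "regardless of whether or not they participate in the study". Section F also takes daily postoperative data and adverse-outcome data from the electronic record. It mentions case report forms, and data "automatically collected via the Regional Anesthesia Outcomes Database and uploaded to that same database", as routes into the study database, without saying which outcomes they supply.

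**The concern.** A between-group test of event proportions is interpretable only if both groups could have the event and if it was looked for in much the same way. Neither condition is secured here.

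First, a patient without a block cannot have a catheter event or become unstable during block placement. The zeros in the control group are structural, so the test on these items measures whether a block was placed, not whether BESB patients fared worse overall.

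Second, some events can occur in either group, such as hypotension or arrhythmia. For these, extra daily assessment can put entries into the BESB chart that routine care would not have produced for a control. Better matching or covariate adjustment does not remove an error of this kind, because it lies in the measurement and not in who was selected.

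Both problems push the same way: BESB looks less safe than it is. At stake is the safety comparison of a technique that Section N says may go forward to a randomized trial.

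**Working it through.** **Inputs.** 45 BESB patients and 90 controls (Sections D(1) and L); two-group Fisher's exact test with significance at P<0.05 (Section K). The plan gives no expected adverse-event rate, no capture rate and no power figure for this test, so there is no figure of its own to reproduce.

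**Step 1: structural zeros.** Suppose x of 45 BESB patients and 0 of 90 controls have an event. Given x events in total, the chance that all fall in the BESB group under the null is C(45, x) / C(135, x). For x = 2 and x = 3 every other split is more probable, so this is also the two-sided p-value.

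- x = 2: 990 / 9,045 = 0.109, not significant.
- x = 3: 14,190 / 400,995 = 0.035, significant.

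Three block-related events are therefore enough, with no difference in any event that controls could have had. The halting rules do not prevent this: for minor or moderate events they act on more than 2 in one patient or more than 10 in aggregate, so three patients with one such event each would not halt enrollment.

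How often would three or more patients be affected? With a per-patient risk q, this is 1 − P(0) − P(1) − P(2) for a binomial with n = 45. The plan gives no q, so these values are assumed:

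- q = 5%: 1 − 0.099 − 0.236 − 0.273 = 0.39.
- q = 10%: 1 − 0.009 − 0.044 − 0.107 = 0.84.

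**Step 2: events possible in both groups.** Let the true risk p be equal in the two groups, BESB capture be complete, and control capture be c. Recorded events are then Binomial(45, p) and Binomial(90, p × c). The probability of every pair of counts is added up over those where Fisher's two-sided p < 0.05 and the BESB proportion is higher. Both p and c are assumptions.

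| True risk | c = 100% | c = 90% | c = 80% | c = 70% | c = 50% |
|---|---|---|---|---|---|
| 10% | 2.1% | 3.3% | 5.1% | 7.7% | 17.0% |
| 20% | 2.0% | 3.8% | 6.9% | 12.0% | 31.6% |
| 30% | 1.9% | 4.4% | 9.2% | 17.7% | 48.0% |
| 40% | 2.1% | 5.5% | 12.6% | 25.2% | 63.9% |

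With equal capture the rate of false BESB excess is about 2%. At 90% control capture it is 3.3% to 5.5%, and at 80% it is 5.1% to 12.6%. The large values need control capture well below that.

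**Step 3: which outcomes are exposed.** The events tracked under Section I are, apart from death, block-related, and the daily assessment is for ropivacaine effects. Neither mentions nausea or vomiting. The extra surveillance therefore bears on adverse events, and Section K assigns its Fisher test to adverse events.

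**The case against.** The strongest reply is that the plan already provides a common source. Section E says its listed items are "collected automatically (via the electronic medical record) for all patients, as a part of their routine clinical care", and that list includes nausea and vomiting, adverse events and STS indices. Section F again names the electronic record for adverse-outcome data. Enrolled patients belong to the same ERAS program as the controls, and analysing records retrospectively does not show that they were charted less completely. Any bias would also count against BESB, so it could not manufacture a benefit.

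Much of this stands. A reader might infer from Sections D(3) and F that BESB and control outcomes come from different databases, and that comparisons of complications and of nausea and vomiting are therefore biased. The documents do not support that. Section F assigns no outcome to the case report forms or the regional anesthesia database, and Section E names one source for everyone.

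Two things survive. A shared record makes the place of storage equal, but not how actively events were sought before being charted. And no shared source can give controls a catheter event. The Section E note is also too broad to serve as a source rule for each outcome: the list it covers includes actigraphy, which Section B limits to the BESB group, and events during block placement.

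**Conclusion.** The point holds for the adverse-event comparison only. The structural-zero problem needs no assumption about capture: on the Section E definition, 3/45 against 0/90 is significant at p = 0.035. How often that would happen depends on a block-event risk that the plan does not give.

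The surveillance problem is a possible bias, not a demonstrated one. If control capture were 80%, a false BESB excess would occur in about 5% to 13% of trials for true risks of 10% to 40%, against about 2% with equal capture. This rests on assumed risks, assumed control capture and complete BESB capture.

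Unequal capture of nausea and vomiting is not shown. The primary opioid endpoint and the sample size are unaffected. The change is worth making because the test as written can yield a misleading safety finding and is cheap to correct.

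**What to change.** In Section K, limit the between-group Fisher test to events that can occur in both groups and are coded by one standard, namely STS-defined complications. State there and in Section F that these are extracted for both groups from the same EMR/STS fields, with one definition and one time window. Report catheter events, placement events and events found by active tracking descriptively for BESB only, as counts and proportions. Leave the halting rules as they are.

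The cost is a wording change and one common query run for both groups. The small downside is that events found only through active tracking are described and not tested.

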## **G. Data Management Methods**

All relevant information retrieved from the electronic medical record, by the PI and/or a member of the research team will be translated into an electronic form. Data collected on paper case report forms will be entered into a standard, secured database for intake and checking, and will be protected by encryption and password. Only authorized users are permitted access to the data files, and daily server back-up activities are executed to ensure data safety. All data will be stored on a password-secured research computer, and all data entered into the computers will be password protected. Procedures to ensure accurate and reliable data collection will include well-designed data forms and training.

## **H. Study Timeline**

We plan to enroll a total of 45 patients in this single arm, open label, interventional study. We anticipate that it will take approximately 2 years to complete enrollment and data collection for this study.

## **I. Adverse Event Criteria and Reporting Procedures**

Adverse or unanticipated events will be reported as required to the Boston Children's Hospital IRB by the PI according to institutional reporting requirements.

An Adverse Event refers to any untoward medical occurrence whether or not it is considered intervention-related.

As noted above, analysis of the retrospective outcomes data for the 45 BCH patients treated with ESBs, the patients in our trial study, and the national and international literature demonstrates no evidence that this block type is associated with any greater risk than that demonstrated by aggregate block data from the various pediatric regional anesthesia registries. Information currently available suggests that regional blockade (including the erector spinae block), when performed properly, carries a very low risk of morbidity and mortality in appropriately selected infants and children.

Nevertheless, as there exist little prospective outcomes data related to the ES block, we will implement a rigorous system to follow and report any adverse events, including interim analyses by a non-blinded statistician, as described below:

### **Adverse Event Monitoring:**

Adverse outcomes will be carefully tracked for all patients enrolled in the study. Enrollment will be halted and the IRB informed by the PI if any of the following conditions are met:

- 1 of any of the following serious adverse events.
  - Patient death.
  - Pneumothorax directly resulting from placement or removal of the blocks and catheters as evidenced by: 1- lung puncture during placement resulting in a moderate to large pneumothorax on the side affected performed within 8 hours, and/or the development of a new air leak in an existing chest tube collection system. 2- The development of a new moderate to large pneumothorax within 8 hours after removal of Erector Spinae plane catheters.
  - Hematoma at the site of the catheter/block—causing pain or any neurological symptoms for the patient.
  - Persistent neurologic symptoms lasting more than 3 days after a single shot block or catheter is removed.

- Local anesthetic systemic toxicity (any symptoms leading to this diagnosis by a study team participant)
- >2 of any of the following minor/moderate adverse events in a given patient or >10 in aggregate:
  - Persistent bleeding at the site of the catheter insertion or block placement.
  - Leakage of local anesthetic from the catheter insertion site that leads to discontinuation of the catheter infusion.
  - Redness or superficial infection of the catheter site or site of the block placement.
  - Skin irritation at the site of the catheter insertion or block placement that results in greater than 3 cm of induration or is associated with pain.

In addition to these stoppage rules, we plan to have [name] MD (Director of Quality and Safety, Cardiac Surgery, BCH) independently review the case outcomes, etc. to ensure patient/subject safety in a way that may not be captured by the above stoppage rules. This monitor will make such assessments for each cohort of 15 patients. As [name] is not a part of the study team, these reviews need not be blinded/redacted/etc. in any way. Any concerns raised by [name] will be brought to the attention of the PI directly and the IRB as well in a timely fashion.

If there is a pause for any of the above reasons, continuance of the protocol will be at the discretion of the IRB in consultation with the study team. No individual care data will be reported unless there is a serious adverse effect. Reports will be done in an aggregated fashion.

*Special note regarding ropivacaine:*

Ropivacaine use constitutes the standard of care at BCH for all nerve blocks and regional anesthetics, including cardiac surgical ERAS patients. Known potential adverse consequences of this mode of delivery of this medication include hypersensitivity, allergic reaction, hypotension and cardiac arrhythmias if injected intravascularly. The presence of any of these will be assessed by the primary anesthesiologist intraoperatively and treated appropriately at the time of block placement and initial bolus and further assessed for such daily by members of the research team and Acute Pain Service. Any occurrence of a possible adverse event or events will be documented and reported to the DSMB, the IRB and the Department of Anesthesia Quality Assurance Physician as appropriate. In the event

of a serious adverse event, it will be reported to the DSMB and IRB immediately and the study halted until a thorough investigation into the cause can be made.

The relative safety of ropivacaine for use in regional anesthesia is supported by the information contained the Pediatric Regional Anesthesia Network (PRAN) database. The PRAN is a consortium of major pediatric centers in North America that manages a prospective data registry on pediatric regional anesthesia. From their database, which at this time comprises more than 130,000 pediatric regional anesthetics from numerous major centers in the US and Canada, ropivacaine is documented to be used in greater than 85% of pediatric regional with a safety profile at least equivalent to, if not better than, bupivacaine.

Further, ropivacaine is very well studied in pediatrics. There is an extensive body of prospective clinical trials and clinical outcomes studies on ropivacaine pharmacokinetics, safety and clinical outcomes from infancy through adolescence. Our prescribing practices at BCH in the Regional Anesthesia and Acute Pain Services are derived from that body of PK information and consensus recommendations.

We therefore regard ropivacaine as the established standard of care for pediatric regional anesthesia and have selected it for use in this study.

